5.5.5 Analysis of Pharmacokinetic/Pharmacodynamic Parameters

The plasma PK of *acalabrutinib* will be characterized using noncompartmental analysis. The following PK parameters will be calculated, whenever possible, from plasma concentrations of *acalabrutinib*:

- AUC_{0-t} Area under the plasma concentration-time curve calculated using linear trapezoidal summation from time 0 to time t, where t is the time of the last measurable concentration (C_t).
- AUC_{0-12} Area under the plasma concentration-time curve from 0 to 12 hours, calculated using linear trapezoidal summation.
- $AUC_{0-\infty}$ Area under the plasma concentration-time curve from 0 to infinity, calculated using the formula: $AUC_{0-\infty} = AUC_{0-t} + C_t / \lambda_z$, where λ_z is the apparent terminal elimination rate constant.
- $AUC_{0-24calc}$ Area under the plasma concentration-time curve from 0 to 24 hours, calculated by doubling the value for AUC_{0-12} .
- C_{max} Maximum observed plasma concentration
- T_{max} Time of the maximum plasma concentration (obtained without interpolation)
- $t_{1/2}$ Terminal elimination half-life (whenever possible)
- λ_z Terminal elimination rate constant (whenever possible)
- CL/F Oral clearance

Missing dates or times may be imputed for PK and PD samples if the missing values can be established with an acceptable level of accuracy based on other information obtained during the visit in question. If PK and PD sampling for a given subject is not performed according to protocol instructions, the subject may be excluded from the PK and PD analyses.

The PK parameters will be tabulated and summarized using descriptive statistics.

For each PD variable, the concentration at each assessment will be described. The change from baseline to each assessment will be summarized. The best change from baseline during the study will also be summarized. As appropriate, the on-treatment values will be compared with the pretreatment baseline values using paired t-tests. P-values of ≤ 0.05 will be considered significant.

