3.5.3 Administration of Study Drug

Investigators are prohibited from supplying *acalabrutinib* to any subjects not properly enrolled in this study or to any physicians or scientists except those designated as subinvestigators on FDA Form 1572. The investigator must ensure that subjects receive *acalabrutinib* only from personnel who fully understand the procedures for administering the drug.

Acalabrutinib is intended to be administered orally with 8 ounces (approximately 240 mL) of water. Subjects may take study drug with or without food. The capsules should be swallowed intact and subjects should not attempt to open capsules or dissolve them in water. Dietary restrictions are provided in [Section 3.7.1](#).

Doses should be taken BID with the second dose 11-13 hours after the first.

If a dose is missed, it can be taken within 3 hours after the scheduled time with a return to the normal schedule with the following dose. If the time from the scheduled time of administration has been > 3 hours, the dose should not be taken, and the subject should take the next dose at the scheduled time. The missed dose will not be made up and must be returned to the site at the next scheduled visit.

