4.1.19 Pharmacokinetics

Refer to the laboratory manual for instructions on collecting and processing these samples. Testing will be performed at a central clinical laboratory. Leftover plasma samples may be used for exploratory *acalabrutinib* metabolite analyses. The predose sample can be taken up to 1 hour before dosing.

Table 4-1. Pharmacokinetic Sample Schedule

| Cycle | Day | HOURS POSTDOSE | | | | | | |
|-------|------------------|--|-----------------|---------------|---------------|----------------|----------------|---------------------------------|
| | | Predose | 0.5 (±5 min) | 1 (±5 min) | 2 (±5 min) | 4 (±10 min) | 6 (±10 min) | 24 (±30 min) |
| 1 | 1 | X | X | X | X | X | X | X*before Day 2 first dose |
| | 8 | X | X | X | X | X | X | |
| | 15, 22, 28 | Predose and 1 h (±5 min) postdose and 5 to 15 min before electrocar diogram (ECG) | | | | | | |

Note: All timepoints are relative to the morning dose.

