- i. Cycle 1 Day 1 testing does not need to be repeated if screening serum chemistry was done within 7 days of first dose of study drug. Serum chemistry: albumin, alkaline phosphatase, alanine transaminase (ALT), aspartate aminotransferase (AST), bicarbonate, blood urea nitrogen (BUN), calcium, chloride, creatinine, glucose, lactate dehydrogenase (LDH), magnesium, phosphate, potassium, sodium, total bilirubin, total protein, and uric acid.
- j. Urinalysis: pH, ketones, specific gravity, bilirubin, protein, blood, and glucose.
- k. T/B/NK cell count (ie, CD3, CD4, CD8, CD19, CD16/56). During Cycle 5-12, only done end of Cycle 6 and 12.
- l. Serum immunoglobulin: IgG, IgM, IgA. During Cycle 5-12, only done end of Cycle 6 and 12.
- m. A bone marrow aspirate and biopsy will be done at screening. Subjects who have a bone marrow aspirate and biopsy result since completion of their last therapy for DLBCL may use those bone marrow results in lieu of the baseline bone marrow aspirate/biopsy required for this study provided the biopsy/aspirate was done within 60 days before the first dose of study drug. Thereafter, bone marrow aspirate and biopsy will only be required to confirm any complete remission.
- n. Pharmacodynamic (PD) assessments will be done on subjects at sites in the United States. On Cycle 1 Day 1 AND Day 8 the PD samples are drawn predose and 4 hours (\pm 10 minutes) postdose. On Cycle 1 Day 2, Cycle 1 Day 28, and Cycle 2 Day 28, the PD samples are drawn up to 10 minutes predose (ie, the first dose of that day). At the Safety follow-up visit, a PD sample will be collected. Note: Timepoints are relative to the morning dose.
- o. Pharmacokinetic (PK) assessments will be done on subjects at sites in the United States. PK samples for Cycle 1 Day 1 are drawn predose and at 0.5, 1, 2, 4, 6 and 24 h (before first dose on Day 2) postdose. Samples for Cycle 1 Day 8 are drawn predose and at 0.5, 1, 2, 4, and 6 h postdose. On Cycle 1 Day 15, 22, and 28, a PK sample is drawn predose and the second PK sample must be drawn 1 hour postdose. Note: Timepoints are relative to the morning dose.
- p. Available archival tumor tissue is required to be eligible for this study. Either unstained slides (a minimum of 10 slides) or a paraffin block will be acceptable for central pathology review.
- q. ***Acalabrutinib*: For Cycle 1 Day 1, 2, 8, 15, 22, and 28 study drug (first dose of the day) is administered at the site.**

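### AUC0-12, and the AUC0-24calc doubled from it, cannot be calculated by the stated method from the stated samples: nothing is drawn between 6 h and 24 h, and the 24 h sample follows the evening dose.

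*Protocol*

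**What the plan says.** Section 5.5.5 of the protocol, repeated in the synopsis, introduces the PK list with "The following PK parameters will be calculated, whenever possible, from plasma concentrations of" acalabrutinib. AUC0-12 is defined as "Area under the plasma concentration-time curve from 0 to 12 hours, calculated using linear trapezoidal summation". AUC0-24calc is twice AUC0-12. AUC0-t uses linear trapezoids to the last measurable concentration Ct, and AUC0-inf adds Ct/lambda_z. Half-life, lambda_z and CL/F are listed without saying which samples enter lambda_z or which AUC enters CL/F.

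Table 4-1 (Section 4.1.19) and Appendix 4, footnote o, agree on the samples:

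- Day 1: "drawn predose and at 0.5, 1, 2, 4, 6 and 24 h (before first dose on Day 2) postdose". Table 4-1 marks the 24 h sample "before Day 2 first dose".
- Day 8: "Samples for Cycle 1 Day 8 are drawn predose and at 0.5, 1, 2, 4, and 6 h postdose".
- Days 15, 22 and 28: "a PK sample is drawn predose and the second PK sample must be drawn 1 hour postdose".

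All times count from the morning dose. On dosing, Section 3.5.3 says: "Doses should be taken BID with the second dose 11-13 hours after the first". No PK day is exempt from the evening dose.

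**The concern.** A linear trapezoid from 0 to 12 h needs a concentration at or beyond 12 h from the same dosing interval. The schedule supplies none on any day. The one later sample, at 24 h on Day 1, belongs to the interval opened by the evening dose.

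Describing the PK of acalabrutinib is the first secondary objective (Section 2.2). As written, a programmer must leave AUC0-12 empty, join 6 h to 24 h across a dose, or invent a rule. These give different numbers under the same parameter name, and a reader of the report could not tell which was used.

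**Working it through.** **Structural check (no assumptions).** The plan states no PK figure to reproduce, so the first step is to set method and schedule side by side.

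- Day 8: the last sample is at 6 h, so trapezoids cover half of the 12 h interval. The stated AUC0-12 does not exist.
- Day 1: the only segment reaching 12 h runs from 6 h to 24 h, with the evening dose at 11 to 13 h inside it.
- Day 1 AUC0-t: if the 24 h value is measurable it is Ct by definition, so AUC0-t spans two doses. AUC0-inf, built on AUC0-t and Ct, inherits this.

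**Size (illustrative).** Assumptions, none from the protocol: one-compartment oral model without noise, ka 2 to 3 per hour, half-life 1 to 3 h, evening dose at 12 h, concentrations scaled so that dose x F / V = 1. Then C(t) = [ka/(ka - ke)] x [exp(-ke t) - exp(-ka t)], with ke = ln 2 / half-life. The 24 h value is C(24) + C(12).

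Example with ka = 3 and half-life 2 h:

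- Linear trapezoids to 6 h give 2.457. C6 = 0.1413 and C24 = 0.0179.
- The 6-to-24 h line read at 12 h is 0.1413 + (0.0179 - 0.1413) x 6/18 = 0.1002.
- The line's 6 to 12 h area is (0.1413 + 0.1002)/2 x 6 = 0.725, against a true 0.357.
- AUC0-12 is 2.457 + 0.725 = 3.182, against a true 2.834: about +12%.
- AUC0-t is 2.457 + (0.1413 + 0.0179)/2 x 18 = 3.890. Single-dose AUC0-inf is 1/ke = 2.885, so +35%. The true two-dose 0 to 24 h area is 5.719, so -32%.
- Proposed rule: lambda_z from 2, 4 and 6 h is 0.3453. The tail is (0.1413/0.3453) x [1 - exp(-6 x 0.3453)] = 0.358. AUC0-12 is 2.457 + 0.358 = 2.815: -0.7%.

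Ranges over ka 2 to 3 per hour:

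| Half-life | Day 1 AUC0-12, 6-to-24 h line | AUC0-t vs single-dose AUC0-inf | AUC0-t vs true 0-24 h area | Day 1 AUC0-12, proposed rule | Day 8, predose as 12 h value |
|---|---|---|---|---|---|
| 1 h | +5.5% to +7.1% | +11% to +14% | -44% to -43% | +0.4% to +1.2% | +2.7% to +3.8% |
| 2 h | +12.2% to +13.4% | +35% to +37% | -32% to -31% | -0.7% to -0.3% | +3.5% to +4.0% |
| 3 h | +12.6% to +13.3% | +43% to +45% | -26% to -24% | -0.9% to -0.5% | +2.5% to +2.8% |

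AUC0-24calc carries the same relative error as AUC0-12. Moving the evening dose to 11 or 13 h changes the AUC0-12 error by less than one percentage point. The part of AUC0-12 that no sample supports (6 to 12 h) is about 2%, 13% and 22% of the total at half-lives of 1, 2 and 3 h (ka = 3). Extending the range to 6 h at ka = 3 gives +9.6% for the 6-to-24 h line and +0.7% for predose as the 12 h value.

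**The case against.** The parameters are promised only where possible, an analysis plan not shown may settle the details, and Section 5.5.6 allows further PK analyses. The choice of samples for lambda_z in particular is normally left to such a plan. All of that is fair for details the protocol leaves open. It does not cover this point: the protocol itself fixes interval, method and schedule, and they fail together in every subject rather than in the odd subject with a missed sample. A plan that extrapolated with lambda_z would depart from the stated trapezoidal rule.

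The limits on size stand. With a short half-life the AUC0-12 error is small. If the 24 h value is below quantification, AUC0-t stops at 6 h and the effect on AUC0-inf, half-life and CL/F disappears; in the model the 24 h value is only 0.05% to 0.07% of Cmax at a half-life of 1 h. The assay limit is not in the protocol.

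A reader might infer more than the protocol supports:

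- **That every PK parameter derives from AUC0-12.** Only AUC0-24calc does. The others are reached, if at all, through the 24 h sample.
- **That half-life is overstated (2.7 to 8.3 h in the model), AUC0-inf by up to 66%, and CL/F understated by 10% to 40%.** Those figures require lambda_z fitted through 4, 6 and 24 h, a choice the protocol does not state. With Ct and lambda_z taken from samples up to 6 h, AUC0-inf is within about 1%.
- **That Day 1 exposure is simply overstated.** For AUC0-t the sign depends on the comparator.
- **That a false fall in exposure from Day 1 to Day 8 would be reported.** No such comparison is planned.

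**Conclusion.** The mismatch is certain and rests on the text alone. AUC0-12 and AUC0-24calc cannot be obtained as stated on Day 8, and on Day 1 only by a line drawn across the second dose. When the 24 h value is measurable, AUC0-t is neither a single-dose area nor a valid 0 to 24 h area, and AUC0-inf inherits that. Half-life is affected only if lambda_z uses the 24 h point, and CL/F only if it uses an affected AUC. Cmax and Tmax are sound.

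The percentages rest on the assumed model and half-life and show an order of magnitude only. Severity is moderate: safety is the primary objective, PK is secondary, summarised descriptively and collected only at US sites (Section 3.2.3), and the protocol ties no decision to an AUC.

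**What to change.** Amend Section 5.5.5 and the synopsis, and carry the wording into any PK analysis plan:

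1. Treat the Day 1 24 h sample as a trough after the evening dose. Exclude it from AUC0-12, AUC0-t, lambda_z, AUC0-inf, half-life and CL/F.
2. Define AUC0-12 as the linear-trapezoid AUC0-6 plus (C6/lambda_z) x [1 - exp(-6 lambda_z)], with lambda_z from the samples up to 6 h. In the model this is within about 1% of truth. On Day 8 the steady-state predose concentration may instead serve as the 12 h value (about +1% to +4%). State which rule applies. Linear trapezoids can stay; a switch to log-linear is not needed.
3. Label the 6 to 12 h part as extrapolated, show AUC0-6 alongside it, and report AUC0-24calc only for Day 8 and only in subjects actually dosed BID, since doubling presumes two equal intervals.

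The cost is wording only, with no added samples or visits. The downside is that part of AUC0-12 is extrapolated rather than observed, which the label and the AUC0-6 column make visible.

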5.5.6 Explorative or Correlative Analyses

Additional PK or PD analyses may be performed, as deemed appropriate.

Correlations between subject characteristics and outcome measures and correlations among outcomes measures will be explored using regression models or other appropriate techniques.

6.0 ASSESSMENT OF SAFETY

Safety assessments will consist of monitoring and recording AEs and SAEs; measurements of protocol-specified hematology, clinical chemistry, urinalysis, and other laboratory variables; measurement of protocol-specified vital signs; and other protocol-specified tests that are deemed critical to the safety evaluation of the study drug(s).

6.1 DEFINITIONS

6.1.1 Adverse Events

An AE is any unfavorable and unintended sign, symptom, or disease temporally associated with the use of an investigational (medicinal) product or other protocol-imposed intervention, regardless of attribution.

This includes the following:

- AEs not previously observed in the subject that emerge during the protocol-specified AE reporting period, including signs or symptoms associated with DLBCL that were not present before the AE reporting period (see [Section 6.2.1](#))

- Complications that occur as a result of protocol-mandated interventions (eg, invasive procedures such as biopsies)
- Preexisting medical conditions (other than the condition being studied) judged by the investigator to have worsened in severity or frequency or changed in character during the protocol-specified AE reporting period.

Abnormal laboratory values should not be reported as AEs; however, any clinically significant laboratory values (defined as requiring treatment, discontinuation from the study, or dose modification) should be reported as AEs.

6.1.2 Serious Adverse Event

The terms “severe” and “serious” are not synonymous. Severity (or intensity) refers to the grade of an AE (see below). “Serious” is a regulatory definition and is based on subject or event outcome or action criteria usually associated with events that pose a threat to a subject’s life or functioning. Seriousness (not severity) serves as the guide for defining regulatory reporting obligations from the sponsor to applicable regulatory authorities.

An AE should be classified as an SAE if it meets any 1 of the following criteria:

- It results in death (ie, the AE actually causes or leads to death).
- It is life-threatening (ie, the AE, in the view of the investigator, places the subject at immediate risk of death. It does not include an AE that, had it occurred in a more severe form, might have caused death).
- It requires or prolongs in-patient hospitalization.
- It results in persistent or significant disability/incapacity (ie, the AE results in substantial disruption of the subject’s ability to conduct normal life functions).
- It results in a congenital anomaly/birth defect in a neonate/infant born to a mother exposed to the investigational product.
- It is considered a significant medical event by the investigator based on medical judgment (eg, may jeopardize the subject or may require medical/surgical intervention to prevent 1 of the outcomes listed above).

6.1.3 Severity

Definitions found in the CTCAE version 4.03 or higher will be used for grading the severity (intensity) of AEs. The CTCAE displays Grades 1 through 5 with unique clinical descriptions of severity for each referenced AE. Should a subject experience any AE not listed in the CTCAE, the following grading system should be used to assess severity:

- Grade 1 (Mild AE) – experiences which are usually transient, requiring no special treatment, and not interfering with the subject’s daily activities

- Grade 2 (Moderate AE) – experiences which introduce some level of inconvenience or concern to the subject, and which may interfere with daily activities, but are usually ameliorated by simple therapeutic measures
- Grade 3 (Severe AE) – experiences which are unacceptable or intolerable, significantly interrupt the subject's usual daily activity, and require systemic drug therapy or other treatment
- Grade 4 (Life-threatening or disabling AE) – experiences which cause the subject to be in imminent danger of death
- Grade 5 (Death related to AE) – experiences which result in subject death

6.1.4 Adverse Events of Special Interest

The following events are adverse events of special interest (AESIs) and must be reported to the sponsor expeditiously (see [Section 6.2](#) for reporting instructions), irrespective of regulatory seriousness criteria or causality:

- *Ventricular arrhythmias (e.g., ventricular extrasystoles, ventricular tachycardia, ventricular arrhythmia, ventricular fibrillation)*

6.2 DOCUMENTING AND REPORTING OF ADVERSE AND SERIOUS ADVERSE EVENTS

The investigator is responsible for ensuring that all AEs and SAEs that are observed or reported during the study, as outlined in the prior sections, are recorded on the eCRF. All SAEs also must be reported on the SAE/Product Compliant form (see [Section 6.2.5](#)).

6.2.1 Adverse Event Reporting Period

After the signing of the ICF and prior to the first dose of study drug, all SAEs must be reported. After the first dose of study drug, all AEs/SAEs, irrespective of attribution of causality, must be reported.

All adverse events will be reported until 30 days after the last dose of study drug or the start of new anticancer therapy (whichever comes first). After this period, investigators should report serious adverse events or other adverse events of concern that are believed to be related to prior treatment with study drug.

All SAEs that occur during the reporting period should be followed to resolution or until the Investigator assesses the subject as stable or until the subject is lost to follow-up or withdraws consent. Resolution/stable means the subject has returned to baseline state of health or the investigator does not expect any further improvement or worsening of the event.

6.2.2 Assessment of Adverse Events

Investigators will assess the occurrence of AEs and SAEs at all subject evaluation timepoints during the study. All AEs and SAEs whether volunteered by the subject, discovered by study personnel during questioning, or detected through physical examination, or other means will be recorded in the subject's medical record and on the AE eCRF and, when applicable, on an SAE/Product Compliant form.

Disease progression itself is not considered an AE; however, signs and symptoms of disease progression may be recorded as AEs or SAEs.

Symptomatic deterioration may occur in some subjects. Symptomatic deterioration is when progression is evident in the subject's clinical symptoms and the investigator may elect not to perform further disease assessments.

Each recorded AE or SAE will be described by its duration (ie, start and end dates), severity, regulatory seriousness criteria, if applicable, suspected relationship to the study drug (see following guidance), and any actions taken. The relationship of AEs to the study drug will be assessed by means of the question: 'Is there a reasonable possibility that the event may have been caused by the study drug?' Answer Yes or No.

See [Appendix 3](#) for more detail on assessing relationship.

6.2.3 Second Primary Malignancies

Adverse events (AEs) for malignant tumors reported during a study should generally be assessed as serious AEs (SAEs). If no other seriousness criteria apply, the "Important Medical Event" criterion should be used. In certain situations, however, medical judgment on an individual event basis should be applied to clarify that the malignant tumor event should be assessed and reported as a nonserious AE. For example, if the tumor is included as medical history and progression occurs during the study but the progression does not change treatment and/or prognosis of the malignant tumor, the AE may not fulfill the attributes for being assessed as serious, although reporting of the progression of the malignant tumor as an AE is valid and should occur. Also, some types of malignant tumors, which do not spread remotely after a routine treatment that does not require hospitalization, may be assessed as nonserious; examples in adults include Stage 1 basal cell carcinoma and Stage 1A1 cervical cancer removed via cone biopsy.

The above instruction applies only when the malignant tumor event in question is a new malignant tumor (i.e., it is not the tumor for which entry into the study is a criterion and that is being treated by the investigational product [IP] under study and is not the development

of new or progression of existing metastasis to the tumor under study). Malignant tumors that—as part of normal, if rare, progression—undergo transformation (e.g., Richter's transformation of B cell chronic lymphocytic leukemia into diffuse large B cell lymphoma) should not be considered a new malignant tumor.

6.2.4 Pregnancy

The investigator should report all pregnancies in study subjects and in the partners of subjects within 24 hours using the Pregnancy Report Form. This form should be faxed or emailed to Acerta Pharma Drug Safety. Any pregnancy-associated SAE must be reported using the SAE report form, according to the usual timelines and directions for SAE reporting ([Section 6.2.5](#)).

Any uncomplicated pregnancy that occurs in a study subject or a partner of a treated subject during this study will be reported for tracking purposes only, if agreed to by the subject or the partner of the subject in this study. All pregnancies and partner pregnancies that are identified during or after this study, wherein the estimated date of conception is determined to have occurred from the time of consent to 30 days after the last dose of study medication will be reported, followed to conclusion, and the outcome reported, as long as the subject or partner is willing to participate in follow-up.

Pregnancy itself is not regarded as an AE unless there is suspicion that the investigational product under study may have interfered with the effectiveness of a contraceptive medication. Likewise, elective abortions without complications are not considered AEs. Any SAEs associated with pregnancy (eg, congenital abnormalities/birth defects/spontaneous miscarriages or any other serious events) must additionally be reported as such using the SAE/Product Complaint form.

Subjects should be instructed to immediately notify the investigator of any pregnancies. Any female subjects receiving *acalabrutinib* who become pregnant must immediately discontinue study drug. The investigator should counsel the subject, discussing any risks of continuing the pregnancy and any possible effects on the fetus.

